11 STATISTICAL CONSIDERATIONS

11.1 Study Hypothesis

The primary objective of this study is to determine the relationship between DHA exposures following IV dosing and markers of physiologic dysfunction associated with severe malaria. This objective can be framed as a series of statistical hypothesis tests, each evaluating the effect of the DHA exposure parameter on the marker of physiologic dysfunction, measured at a specific timepoint, while adjusting for covariates. The null hypothesis is that there is no effect of exposure on response, and the alternative hypothesis is that there is an effect. The secondary objectives can be framed in an analogous manner, with time to hospital discharge and measures of parasite clearance as the response variables.

11.2 Sample Size Considerations

A maximum of 100 subjects would provide sufficient sample size to achieve precision on PK parameters following the FDA pediatric precision criteria for conducting PK studies (achieving a 95% confidence interval (CI) within 60% and 140% of the geometric mean).

Simulations in R version 3.4.2 were used to explore power to detect simple linear relationships between exposure and response in the analysis of the primary objective with the planned sample size. The primary objective of this study encompasses multiple exposure and response variables, and the response variables are measured at multiple timepoints. Thus, there are multiple exposure-response relationships that are of interest (one for each unique combination of exposure variable, response variable, and timepoint), and there is a need to control type I error. As this study is exploratory (hypothesis-generating) rather than confirmatory, Benjamini-Hochberg procedure is used to control the false discovery rate at 0.05 (Benjamini 1995).

For a multiple hypothesis test, average power is defined as the proportion of false null hypotheses that were correctly rejected (Benjamini 1999). Table 11.1 provides the average power computed from 5000 simulations, varying the following quantities:

[figure not shown]
- Number of total statistical tests, representing the number of combinations of exposure variable, response variable, and timepoint to be tested in support of the primary objective
- Value of R^2 for the true, non-null exposure-response relationships
- Proportion of tests with true, non-null exposure-response relationships with the specified R^2
- Sample size

Table 11.1: Average Power for Identifying Simple Linear Exposure-Response Relationships

Number of Tests	R ²	Proportion of Tests with Specified R ²	Power for N=100 Subjects	Power for N=80 Subjects
24	0.2	0.05	0.95	0.88
48	0.2	0.05	0.95	0.88
24	0.2	0.10	0.97	0.92
48	0.2	0.10	0.98	0.92

Simulation results indicate that the target sample size of 100 subjects provides >90% power for detecting simple linear relationships with an underlying R² of at least 0.2, if the proportion of non-null relationships among those tested is at least 5%. If only 80 subjects complete follow-up for the primary endpoint, power for the same scenario is approximately 88%.

Figure 11.1: Example Data with R² = 0.2 and N=100 Observations

11.3 Final Analysis Plan

Further details on the analyses discussed below will be provided in the Statistical Analysis Plan (SAP), which will be finalized prior to data lock. In case the language in this section differs from the language in the SAP, the SAP will take precedence.

11.3.1 Analysis of Demographics and Baseline Characteristics

Demographic characteristics (age, sex, and town/village of residence) of each participant will be tabulated. Weight-for-age and height-for-age z-scores will be determined based on WHO Child Growth Standards (WHO, 2006). Summary statistics (e.g. mean, range, and standard deviation) of age, weight, height, weight z-score, and height z-score will be tabulated by sex.

11.3.2 Analysis of Safety

The number of subjects experiencing unsolicited AEs, classified using the Medical Dictionary for Regulatory Activities (MedDRA®) System Organ Classes and Preferred Terms, reported throughout the study after study drug administration will be tabulated by severity, and relationship to study product. SAEs will be described. A complete listing of AEs for each subject will provide details including severity, relationship to study drug, onset, duration, and outcome.

11.3.3 Clinical Laboratory Parameters

Hematological and biochemical laboratory parameters will be measured at study days 1, 2, 3, 4, 5, 6 and 7. Clinically relevant abnormal values based on reference intervals determined in a similar population will be tabulated and a trend analysis performed if deemed necessary.

11.3.4 Analysis of Pharmacokinetics of Dihydroartemisinin

Population PK models for DHA have been previously published but have not described the population PK of DHA in critically ill malaria patients and related it to the PD and clinical outcomes in the same analysis. This planned analysis involves use of the data to characterize the PK of DHA in these critically ill pediatric patients, and for the assessment of selected covariates on intersubject variability in the PK of DHA. Overall, the information gained from the planned analyses will support the understanding of exposure-response relationship to support dose regimen selection.

Population PK analyses will be performed using Nonlinear Mixed Effects Modelling (NONMEM) v7.3 or higher, Pumas, or similar software. The general procedure that will be followed for the development of the population PK model is outlined below:

1. Exploratory data analysis

The number of samples per subject and by timing relative to last dose will be summarized. Concentration outliers and other implausible values will be identified using scatterplots. Frequency of below quantification limit (BQL) concentrations will be determined. Outliers detected by exploratory data analysis may be queried prior to data lock and may be flagged for exclusion from analysis if problematic for fitting the model.

2. Base structural model development for PK

One- and two-compartment parent-metabolite models of artesunate and DHA will be considered, as well as one- and two-compartment models that do not explicitly model artesunate since artesunate concentrations will not be measured. Competing models will be distinguished by their objective function value, the plausibility of parameter estimates, and standard diagnostic plots, including observed vs. individual-fitted concentrations, observed vs. population-fitted concentrations and weighted residuals.

3. Evaluation of covariate effects

Allometric scaling will be evaluated using both standard values (0.75 for clearance and 1.0 for volume) and estimated coefficients. Sex and whether the subject had a dose of artesunate prior to enrollment will also be evaluated. Additional covariates for evaluation may be specified in the SAP. Inclusion of covariate relationships in the final model will be based on forward selection, with criteria mainly based on a statistically significant likelihood ratio test but also considering reduction of unexplained between subject variability and improved characteristics seen in diagnostic plots.

4. Final model refinement

Backwards elimination will be used to remove statistically or clinically insignificant covariate relationships. Distributions of individual random effect values will be used to assess outliers or possible subpopulations unaccounted for in the model.

5. Model evaluation

Predictive performance of the final model will be assessed using visual predictive checks and normal prediction distribution error.

11.3.5 Analysis of Pharmacodynamics of Dihydroartemisinin

Analysis Plan for Primary Outcome

The primary outcome response variables are: temperature, serum lactate, serum glucose, acidosis, BCS, total and direct bilirubin, anemia. For each subject, values of the DHA exposure

parameters AUC_{0-12} and C_{max} values for each individual subject and treated as fixed in downstream PD analyses.

Regression methods will be used to characterize the relationship between exposure and responses, while controlling for covariates. For continuous response variables (temperature, serum lactate, serum glucose, acidosis, and anemia), linear, polynomial and E_{max} models with random effects will be considered. BCS is an ordinal scale designed to assess malarial coma in children, with possible values of 0, 1, 2, 3, 4, 5. Proportional odds mixed effects logistic regression will be used to model BCS.

Covariates will include exposure, timepoint, the interaction between exposure and timepoint, and potential confounding variables such as receipt of artesunate or artemisinin-based therapy prior to enrollment. Specific details of all models will be described in the SAP, and will include:

- The precise definition or derivation of each response variable, including potential transformations and the method for accounting for baseline values and/or associations between the baseline value and exposure
- The pre-specified covariates to be included in the model
- The procedure for choosing the covariance structure
- The alternative methods which may be considered, if model assumptions do not hold

For the analysis of the response variables included in the primary outcome, the set of p-values corresponding to tests of the effect of exposure on response at each timepoint will be adjusted using the Benjamini-Hochberg procedure to preserve the false discovery rate for the primary outcome at 0.05. The corresponding point estimates and CIs will be reported. Graphical displays of response by exposure at each timepoint will show individual measurements alongside model estimates. Individual trend plots of responses over time will also be generated for each response variable.

Analysis Plan for Secondary Outcomes

The secondary outcome response variables are time to hospital discharge, and measures of parasite clearance calculated from parasite density, as measured by thick blood smear such as parasite clearance half-life, total parasite clearance by Day 2, and time to 90% reduction in parasitemia. Parasite clearance half-life (PCT₅₀) and time to 90% reduction (PCT₉₀) will be estimated using the WorldWide Antimalarial Resistance Network (WWARN) parasite clearance estimator (PCE) algorithm (Flegg 2011). The relationship between AUC_{0-12} and C_{max} and the time-to-event response variables will be analyzed using Cox proportional hazards regression.

The relationship between AUC_{0-12} and C_{max} and the binary variable of total parasite clearance by Day 2 will be analyzed using logistic regression. Covariates will include exposure and potential confounding variables. The full list of covariates to be considered and the variable selection strategy will be described in the SAP. Analyses of secondary outcome variables will not be adjusted for multiplicity.

11.3.6 Missing Data

Every effort will be made to minimize missing data and collect all endpoints specified in this protocol. Subjects who discontinue treatment will be followed after treatment discontinuation for collection of all scheduled follow-up data with their consent. Sensitivity analyses will be conducted to exclude the subset of subjects who received IV artesunate prior to enrollment. No adjustments for missing safety data will be performed for the secondary analyses. Handling of missing dosing, PK, covariate, and outcome data will be described in the SAP.

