8.2.1.2 Children >6 years of age will not undergo neurodevelopmental assessment

8.3 Laboratory Evaluations

8.3.1 Clinical Laboratory Evaluations

Malaria Diagnostics

Samples for malaria diagnostics will be collected according to the following schedule in hours: 0 (0-2 hour acceptable window), 6 (4-8 hour acceptable window), 12 (10-14 hour acceptable window), 24 (22-26 hour acceptable window), 36 (34-38 hour acceptable window) and 48 (46-50 hour acceptable window), and then parasitemia should be measured at least every 24 hours until clearance. Thick and thin blood smears for malaria diagnosis will be stained with Giemsa stain and read at 100X power light microscope. Parasites will be quantitated by counting the number of asexual *P. falciparum* parasites per 200 WBC using the patient's WBC count per μ L of blood. Thick blood smears will be used for diagnosis and thin blood smears for typing the species of malaria parasites. Thin and thick blood smears will be repeated on all follow up days because the different species of malaria parasites have different incubation periods.

Collection of blood for Artesunate Pharmacokinetic assays

Approximately 10mLs (~2 mL/timepoint) of venous blood will be collected into fluoride-oxalate tubes from the arm opposite of that used for drug administration at 0 (pre-dosing), and 4 times following the first dose in the hospital during different sampling windows. Sampling windows are defined for post-dose collections: 0-1 hour, 1-2.5, 2.5-4, 4-6 and 6-24 hours post-dose.

Participants will be randomly assigned to either the 4-6 hour or the 6-24 hour collection timepoint via the Screening and Enrollment Log. All blood samples will be chilled immediately to prevent artesunate degradation by plasma esterases. Samples will be centrifuged within 30 minutes to minimize hemolysis, and aliquots of plasma will be stored at -80°C (-60°C or colder acceptable). Plasma aliquots will be shipped intermittently to the IDI Core Laboratory for storage prior to quantification. Plasma samples will be assayed by a validated high-performance liquid chromatography (HPLC) method.

Diagnosis of Severe Malaria

Severe malaria is defined as presence or history of fever plus a positive blood film for *P. falciparum* malaria with at least one of the following symptoms and signs:

- Impaired consciousness: A Glasgow coma score < 11 in adults or a Blantyre coma score < 3 in children

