4.5.2. Pharmacokinetics Variables

Blood (plasma) samples will be collected for PK analysis and estimation of DHA exposure parameters. Approximately 10mLs (~2 mL/timepoint) of venous blood will be collected into fluoride-oxalate tubes from the arm opposite of that used for drug administration at pre- and 4 times after the first on-study dose in the hospital during different sampling windows. Sampling windows are defined as 0 (pre-dose), 0-1 hour, 1-2.5, 2.5-4, 4-6 and 6-24 hours post the first on-study dose of IV artesunate. Participants will be randomly assigned to either the 4-6 hour or the 6-24 hour collection timepoint via the Screening and Enrollment Log. All blood samples will be chilled immediately to prevent artesunate degradation by plasma esterases. Samples will be centrifuged within 30 minutes to minimize hemolysis, and aliquots of plasma will be stored at -80°C. Plasma aliquots will be shipped intermittently to the DMID-CMS (i.e., Fisher BioServices) for storage before quantification. Backup samples will be stored at the IDI Core Laboratory. Plasma samples will be analyzed by a validated liquid chromatographic-tandem mass spectrometry (LC-MS/MS) assay with measurement ranging from 1 to 3500 ng/mL (lower limit of quantification [LLOQ] to upper limit of quantification [ULOQ]).

Concentrations of DHA will be measured and used in estimating DHA exposure parameters, including maximum concentration (C_{max}), area under the curve over hours 0-12 (AUC_{0-12}), half-life ($t_{1/2}$) and time to C_{max} (T_{max}).

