6.4. Covariates and Subgroups

Sensitivity analyses for the primary and both secondary analysis outcome measures will be conducted to assess the effect of receipt of IV artesunate or other artemisinin-based therapies before enrollment on results of the primary and secondary analyses. This sensitivity analysis will be conducted on the subset of the PD Analysis Population who did not receive any IV artesunate or other artemisinin-based therapy before enrollment.

Otherwise, the protocol does not define any formal subgroup analyses, and the study is not adequately powered to perform subgroup analyses. However, primary and secondary analyses will be adjusted for

possible confounding factors. The following baseline covariates will be considered for inclusion in all primary and secondary analyses:

- Sex (male or female),
- Weight group (<20 kg or \geq 20 kg),
- Receipt of IV artesunate or artemisinin-based therapy before study enrollment (received no IV artesunate or artemisinin-based therapy before study enrollment or received any IV artesunate or artemisinin-based therapy before study enrollment), and
- Receipt of antimalarial concomitant medications or other concomitant medications with antimalarial properties (received no such concomitant medications or received any such concomitant medications).

Receipt of oral ACT post-enrollment (received no oral ACT or received any oral ACT) will also be considered for inclusion as a covariate in primary analyses at timepoints at which there are participants receiving oral ACT and in secondary analyses. The number of doses of oral ACT received may also be considered for inclusion in these analyses.

Inclusion of covariates in each primary and secondary analysis will be informed by exploratory boxplots and stacked bar graphs of response variables by covariate values, and by timepoint when appropriate (see Section 8 for further details).

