6.5. Missing Data

Every effort will be made to minimize missing data and collect all outcome measures specified in this protocol. Participants who discontinue treatment will be followed after treatment discontinuation for collection of all scheduled follow-up data with their consent.

Missing dose data (dosing time, or dosing date) will be imputed to maximize the inclusion of observations subsequent to doses with missing information. Missing dosing time will be imputed if the dose date and amount are available:

- If dosing times are missing, the pre-dose sample time combined with the dose number and dosing timeline will be used to determine the pre-study and on-study dosing times.
- Dosing time will be imputed as the mean of the time from pre-dose draw to dosing for those not missing the given sampling window.

Missing covariate data for analyses that incorporate confounding covariate variables will be handled in the following manner. The covariate will be excluded from the analysis if more than 20% of the covariate values are missing. Baseline individual covariates, including sex and weight group, will be determined from the Day 1 visit. If an individual's baseline covariate is missing at the Day 1 visit, the baseline covariate value will be taken from either the pre-study (screening) visit or from the earliest post-dose visit, whichever is closest to the baseline visit. Receipt of IV artesunate or artemisinin-based therapy before enrollment will be determined from treatment administration records with dates and times before the first on-study dose and/or concomitant medication records with dates up to the Day 1 visit. Receipt of oral ACT, which has planned collection occurring after baseline, will be determined from all visits up to and including the visit at which the analysis timepoint occurs.

No imputation will be performed for missing primary or secondary PD outcome response variables. Rather, only participants in the PD Analysis Population with the PD outcome response variable measured at the timepoint of interest will be included in PD analyses of that PD outcome response variable measured at the timepoint of interest.

Please refer to the Pharmacometrics Analysis Plan for details pertaining to methods for missing concentration data and other missing data that would affect the PK analysis.

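### Prior artemisinin therapy is classified from records alone; a quantifiable pre-dose DHA level should also count when the covariate and the no-prior-therapy subset are formed

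*Protocol*

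**What the plan says.** The protocol limits the sensitivity analysis to prior IV artesunate (11.3.6): "Sensitivity analyses will be conducted to exclude the subset of subjects who received IV artesunate prior to enrollment". Protocol 11.3 adds that where the two documents differ "the SAP will take precedence". The operative definition is therefore in the SAP. Section 6.4 runs the sensitivity analysis on the "subset of the PD Analysis Population who did not receive any IV artesunate or other artemisinin-based therapy before enrollment".

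SAP 6.5 says how that status is established: "Receipt of IV artesunate or artemisinin-based therapy before enrollment will be determined from treatment administration records". Those records count if they are dated and timed earlier than the first dose given on study. The other source, used alone or in addition, is the concomitant medication records up to the Day 1 visit. Protocol 6.5 and SAP 4.4.7 obtain concomitant medications by asking the parent or guardian, looking back 7 days before enrollment.

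PK blood is drawn "at 0 (pre-dosing), and 4 times following the first dose in the hospital" (Protocol 8.3.1; SAP 4.5.2 refers to the first on-study dose). Plasma goes to an LC-MS/MS "assay with measurement ranging from 1 to 3500 ng/mL" (SAP 4.5.2), and DHA is the analyte. SAP 6.5 uses the time of the pre-dose sample to impute missing dosing times. It gives no use for the concentration measured in it.

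Prior status is also a PK covariate: "Sex and whether the subject had a dose of artesunate prior to enrollment will also be evaluated" (Protocol 11.3.4).

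**The concern.** Pre-treatment is expected by design. Protocol 7.1 allows enrollment up to 24 hours after a first IV artesunate dose, and the only exclusion is more than 24 hours of artemisinin therapy. The prior-therapy flag is a candidate covariate in every primary and secondary model. It alone defines the subset behind Tables 14, 16 and 18, the second population in Figures 35 to 210, and the subset rows of Tables 20 to 28.

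That subset exists to show whether the exposure-response findings depend on earlier artemisinin. If a child's own pre-dose sample contains DHA but no earlier dose was recorded, the stated rule keeps the child in the subset and codes the covariate as no. The plan would then hold evidence against its own classification and have no instruction to act on it. Dealing with such a child after the exposure-response results are known would be a post hoc choice.

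**Working it through.** **1. Is a pre-dose sample in every child's schedule?** SAP 4.5.2 gives about 10 mL in total at about 2 mL per timepoint: 10 / 2 = 5 samples. The schedule is 1 pre-dose + 4 post-dose = 5, so the plan's figure is reproduced. There are five post-dose windows, but each child is randomly assigned to only one of the last two (4-6 h or 6-24 h). Randomization does not touch the pre-dose sample.

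**2. Does any visible rule use the pre-dose concentration to classify?**
- SAP 6.4 and Section 8 define the covariate and the subset by receipt of therapy.
- SAP 6.5 derives receipt from the two kinds of record only.
- SAP 8.1 carries the same subset into the sensitivity models.
- Protocol 11.3.4 screens for concentration outliers and may query or exclude them, and Listing 12 prints individual concentrations. Neither reclassifies a child.

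**3. What would be misclassified?** Baseline (SAP 3.3), the 24 h and 48 h responses (SAP 8.1 and Table 13) and the 50-hour window for clearance by Day 2 (SAP 4.5.1 and 8.2.2) all run from the first dose of IV artesunate.

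| Unrecorded earlier therapy | Covariate and subset | Clock and baseline reference |
|---|---|---|
| IV artesunate | wrong | wrong |
| Other artemisinin-based therapy | wrong | unchanged; the SAP would not move time zero for it even if recorded |

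**4. How far back does the check look?** Assuming one-phase decline, look-back = half-life × log2(peak / LLOQ), with LLOQ = 1 ng/mL from SAP 4.5.2. The documents give no DHA half-life or peak, so both are assumed. The top value of 3500 ng/mL is simply the assay's upper limit.

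| Assumed peak (ng/mL) | log2(peak / 1) | Half-life 0.5 h | 1 h | 2 h |
|---|---|---|---|---|
| 100 | 6.64 | 3.3 h | 6.6 h | 13.3 h |
| 1000 | 9.97 | 5.0 h | 10.0 h | 19.9 h |
| 3500 | 11.77 | 5.9 h | 11.8 h | 23.5 h |

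The range is about 3 to 24 hours. The longest value is 23.5 / 168 = 14% of the 7-day medication history.

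**5. How many children?** The documents give no rate of unreported use, so this is illustration only. Take 75 children (the smallest number in the SAP's 176-test power simulation) and assume 30% are recorded as pre-treated: 75 × 0.70 = 52.5 are classed as untreated. Unreported use of 2%, 5%, 10% or 20% among them gives about 1.1, 2.6, 5.2 or 10.5 misclassified children. The count from the assay could be zero.

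**The case against.** The strongest reply is that the exposure with the most serious consequences is the one least likely to be missed. Children are screened from the emergency department after artesunate has been prescribed (Protocol 7.1). The number of earlier IV doses is documented in the eCRF (SAP 4.4.8), with dates and times in Listing 8. Caregiver recall matters mainly for other therapy, which does not move the clock. This stands, and it limits the point. A reader might infer that the 24 h, 48 h and 50 h responses are generally timed from the wrong dose. The documents do not support that: an error in timing requires an unrecorded IV artesunate dose, and nothing shows that one occurred.

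A second reply is that PK handling belongs to a separate Pharmacometrics Analysis Plan, which is not available here. This also stands: one cannot say that pre-dose DHA goes unused throughout the trial's analysis. But the PD covariate and the subset are defined in the SAP, which refers to that plan for missing concentration data and other gaps affecting PK, not for this classification.

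Third, the check is partial. It reaches back hours, not 7 days, so the remaining subset could not be called artemisinin-naive. The documents describe DHA only as the metabolite of artesunate, so the check covers products that yield DHA, and a positive result does not show the route. Some pre-dose samples may be missing or mistimed, since treatment is not held up for enrollment procedures. These are limits on what the rule can achieve. They are not reasons to ignore a positive result.

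**Conclusion.** The point holds in a limited form. The SAP classifies prior artemisinin therapy from records alone although a more direct check on recent dosing is already scheduled for each child. Under the rule as written, a child with quantifiable pre-dose DHA and no recorded dose is analysed as not previously treated. The certain consequence for such a child is a wrong covariate value and wrong subset membership. A wrong time zero and baseline reference follow only if the missed dose was IV artesunate.

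The size is unknown. The look-back of about 3 to 24 hours rests on assumed peaks of 100-3500 ng/mL and half-lives of 0.5-2 h, and the illustrative counts rest on assumed rates of recorded and unreported use. No error in the sample size, power or multiplicity procedure follows, and the study describes itself as hypothesis-generating. The change is still worth making because it uses data already planned and improves the one sensitivity subset the SAP defines.

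**What to change.** Before database lock, add to SAP 6.5 that a pre-dose DHA concentration at or above the LLOQ also counts as prior artemisinin-based therapy, once the draw time has been queried against the dose time to rule out a sample taken after dosing. Apply the flag to the PD covariate and to exclusion from the no-prior-therapy subset. Where the pre-dose result is missing or its timing cannot be verified, keep the record-based status and say so.

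Add a row to Table 5 for the number of children reclassified by this rule. Align the PK covariate with the Pharmacometrics Analysis Plan so that both analyses use the same definition, or explain why they differ.

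The cost is one derivation rule, one table row and a small number of timing queries; no new sample or assay is needed. The subset may lose a few children, and with them some precision. The text should also state that a result below the LLOQ does not rule out earlier therapy.
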